Statistical Methods for Key Efficacy Analyses	
The primary hypotheses will be evaluated by comparing pembrolizumab in combination with SOC (pomalidomide + low dose dexamethasone) versus SOC (pomalidomide + low dose dexamethasone) on PFS and OS using a stratified log-rank test. Estimation of the hazard ratio will be done using a stratified Cox regression model for each endpoint. Event rates over time will be estimated within each treatment group using the Kaplan-Meier method.
 
The key secondary endpoint ORR will be analyzed using the stratified Miettinen and Nurminen method on the first 210 subjects (~70% of ITT).
						
Statistical Methods for Key Safety Analyses	
The analysis of safety results will follow a tiered approach. The tiers differ with respect to the analyses that will be performed. For this protocol, there are no Tier 1 events. Tier 2 parameters will be assessed via point estimates with 95% confidence intervals provided for between-group comparisons; only point estimates by treatment group are provided for Tier 3 safety parameters. Confidence intervals for between-treatment difference will be provided using the Miettinen and Nurminen method.
						

Interim Analyses	
There are two interim analyses planned for this study. Results will be reviewed by an external data monitoring committee. Details are provided in Section 8.7.
 
 • Interim Analysis (IA) 1 
 ○ Timing: after ~ 210 subjects with 2 cycles of treatment ○ Purpose: To demonstrate the superiority of pembrolizumab in combination with SOC (pomalidomide + low dose dexamethasone) versus SOC (pomalidomide + low dose dexamethasone) in ORR • Interim Analysis (IA) 2 
 ○ Timing: after the target number of PFS events (~ 236) are observed ○ Purpose: 1) To demonstrate the superiority of pembrolizumab in combination with SOC (pomalidomide + low dose dexamethasone) versus SOC (pomalidomide + low dose dexamethasone) in PFS; and 2) To assess the OS of pembrolizumab in combination with SOC (pomalidomide + low dose dexamethasone) versus SOC (pomalidomide + low dose dexamethasone)

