Multiplicity	
The family-wise type I error rate for this study is strongly controlled at 2.5% (one-sided) for the hypothesis testing of ORR, PFS and OS. The multiplicity strategy will follow the graphical approach of Maurer and Bretz (2013) as described in Section 8.8, with 0.5%, 1.5% and 0.5% alpha allocated to the ORR, PFS and OS hypothesis, respectively.
 
For the OS hypothesis, a Hwang-Shih-DeCani alpha-spending function with the gamma parameter (-6) is constructed to implement group sequential boundaries that control the type I error rate. Further details of the interim analysis strategy can be found in Section 8.7.1

Sample Size and Power	
The planned sample size is approximately 300 subjects. The primary endpoints of the study are PFS and OS. For PFS, based on 236 events, the study has ~90.6% power to detect a hazard ratio of 0.635 (pembrolizumab in combination with SOC vs. SOC) at alpha = 1.5% (one-sided). For OS, based on 182 events, the study has ~ 80.5% power to detect a hazard ratio of 0.600 (pembrolizumab in combination with SOC vs. SOC) at alpha = 0.5% (one-sided). For ORR based on the first 210 randomized patients followed for two cycles of treatment or have discontinued earlier, the study has 88.7% power to detect a 25 percentage point increase for pembrolizumab in combination with SOC vs SOC at alpha = 0.5% (one-sided)

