8.5 ANALYSIS POPULATIONS

8.5.1 Efficacy Analysis Populations

The Intention-to-Treat (ITT) population will serve as the population for primary efficacy analysis. All randomized subjects will be included in this population. Subjects will be included in the treatment group to which they are randomized. Details on the approach to handling missing data are provided in Section 8.6 Statistical Methods.

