If sample size permits, response duration will be summarized descriptively using Kaplan-Meier medians and quartiles, results permitting. Only the subset of subjects who show at least a partial response will be included in this analysis. Additional details on the censoring rules for DOR will be provided in the supplemental SAP.

Disease Control Rate (DCR)

The stratified Miettinen and Nurminen will be used for comparison of the DCR between the treatment groups, using sample size weighting. A 95% confidence interval for the difference in disease control rates between the active arms and the standard therapy arm will be provided. Disease status and number of prior treatments will be used as the stratification factors in the analysis.

Second Progression-free Survival (PFS2)

The non-parametric Kaplan-Meier method will be used to estimate the PFS2 curves. The treatment difference in PFS2 will be assessed by the stratified log-rank test. A stratified Cox proportional hazards model with Efron's method of tie handling will be used to assess the magnitude of the treatment difference (ie, the hazard ratio). The hazard ratio and its 95% confidence interval from the stratified Cox model with a single treatment covariate will be reported. Disease status and number of prior treatments will be used as the stratification factors in both the stratified log-rank test and the stratified Cox model. Further details of PFS2 analyses will be described in supplemental SAP.

[Table 15](#) summarizes the primary analysis approach for primary and secondary efficacy endpoints. Sensitivity analysis methods are described above for each endpoint.

Table 15 Analysis Strategy for Key Efficacy Endpoints

Endpoint/Variable (Description, Time Point)	Statistical Method†	Analysis Population	Missing Data Approach
Primary Endpoint			
PFS per IMWG 2011 by CAC blinded central review	Testing: Stratified Log-rank test. Estimation: Stratified Cox model with Efron's tie handling method	ITT	
 • Primary censoring rule • Sensitivity analysis 1 • Sensitivity analysis 2 (More details in Table 14)
OS	Testing: Stratified Log-rank test Estimation: Stratified Cox model with Efron's tie handling method	ITT	
 • Censored at last date known alive
Secondary endpoints			
ORR per IMWG 2011 by CAC blinded central review	Stratified Miettinen and Nurminen method	ITT	Subjects with missing data are considered non-responders

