8.7 INTERIM ANALYSES

8.7.1 Efficacy Interim Analyses

There are two planned interim analyses (IA) for this study. The trial will continue irrespective of the outcome of the two interim analyses. Results will be reviewed by an eDMC.

IA1, which is the final analysis of ORR, will be performed after approximately the first 210 randomized subjects (~70% of the ITT population) are followed for two cycles of treatment or have discontinued earlier.

IA2, which is final PFS analysis and interim OS analysis, will be performed when all subjects are enrolled, and approximately 236 PFS events are observed.

For the hypothesis of OS, a Hwang-Shih-DeCani alpha-spending function with gamma parameter (-6), is used to construct group sequential boundaries to control the type I error rate. The actual boundaries will be determined from the number of deaths observed at the time of the interim analysis for the specified analysis using the alpha-spending function. The Hwang-Shih-DeCani alpha spending function, based on the gamma parameter selected (-6), is more conservative than the O'Brien-Fleming bound recommended by the FDA.

[Table 17](#) summarizes the timing, number of events and decision guidance for the PFS, OS and ORR analyses. The actual boundaries and the alpha level will be determined from the actual number of events observed at the time of the interim analysis using the corresponding alpha-spending function as well as the results of the ORR and PFS analyses (see Section 8.8).

Table 17 Decision Guidance at Each Efficacy Analysis

Analysis	Timing/Criteria for Conduct of Analysis	Testing	Value	Efficacy*
IA1 : ORR	~ 12 months after trial starts (~ 210 subjects randomized + 2 months)	ORR (Superiority): pembrolizumab in combination with SOC vs. SOC	ORR Δ bound [†] p-value (1-sided)	~ 17% ≤ 0.005
IA2: PFS analysis / Interim OS analysis	~ 20 months after trial starts (all subjects randomized and ~ 236 PFS events are observed) OS Events (anticipated): ~ 124	PFS (Superiority): pembrolizumab in combination with SOC vs. SOC	~ HR at bound p-value (1-sided)	0.75 ≤ 0.015
		OS (Superiority): pembrolizumab in combination with SOC vs. SOC	~ HR at bound p-value (1-sided)	0.57 ≤ 0.0007
Final OS analysis	~ 10 months after PFS analysis or ~ 182 OS events are observed, whichever comes first	OS (Superiority): pembrolizumab in combination with SOC vs. SOC	~ HR at bound p-value (1-sided)	0.68 ≤ 0.0048

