8.9 Sample Size and Power Calculations

The study will randomize approximately 300 subjects in a 1:1 ratio among the two treatment arms: pembrolizumab in combination with SOC (combination therapy), and SOC (control).

With ~ 210 subjects at IA1, the study has ~ 88.7% power for detecting a 25% difference in ORR (55% vs. 30%) at 0.5% level of significance (one-sided).

IA2, the final PFS analysis of the study will be performed after approximately 236 PFS events have been observed, and this will occur ~20 months after the first subject is enrolled.

The final OS analysis of the study will be performed 10 months after the PFS analysis or after 182 deaths have been observed in the trial, whichever comes first.

For the primary endpoint PFS, the study has ~90.6% power to detect a hazard ratio of 0.635 (pembrolizumab in combination with SOC vs. SOC) at alpha = 1.5% (one-sided). The sample size calculation is based on the following assumptions: 1) progression-free survival follows an exponential distribution with a median of 4 months in the control arm (Arm B), 2) an enrollment period of 14 months and at least 6 months follow-up, 3) a yearly dropout rate of 5% and 4) ORR is negative.

For the primary endpoint OS, the study has ~80.5% power to detect a hazard ratio of 0.600 (pembrolizumab in combination with SOC vs. SOC) at alpha = 0.5% (one-sided). These calculations are based on the following assumptions: 1) OS follows an exponential distribution with a median of 12.7 months in the control arm (Arm B), 2) an enrollment period of 14 months and at least 16 months follow-up, 3) a yearly dropout rate of 2% and 4) PFS is negative.

The assumed median PFS and OS in the control arm (Arm B) are observed for standard of care in treatment of refractory or relapsed multiple myeloma [46]

The sample size and power calculations were performed in the software EAST 6.

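### The Table 15 ORR row names all randomized subjects (ITT) as the analysis population, while the IA1 test is described, timed and powered on the first 210; read literally, the row dilutes both response rates and costs about 5 to 6 points of power

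*Combined protocol and SAP*

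**What the plan says.** - **Section 8.1 (summary), methods:** "ORR will be analyzed using the stratified Miettinen and Nurminen method on the first 210 subjects (~70% of ITT"). The sample-size entry in the same table also bases ORR on the first 210 randomized patients, followed for two cycles or discontinued earlier.
- **Section 8.6.1, Table 15, ORR row:** stratified Miettinen and Nurminen method, population ITT, and "Subjects with missing data are considered non-responders". The text introducing the table presents it as the primary analysis approach for the primary and secondary efficacy endpoints.
- **Section 8.5.1, defining ITT:** "All randomized subjects will be included in this population".
- **Section 8.7.1:** "IA1, which is the final analysis of ORR, will be performed after approximately the first 210 randomized subjects" have two cycles of follow-up or have discontinued. This fixes when the analysis is done. It does not say that later-randomized subjects are left out.
- **Section 8.9:** "With ~ 210 subjects at IA1", "the study has ~ 88.7% power for detecting a 25% difference in ORR".
- **Section 2.1:** one ORR analysis is planned, and enrollment is not paused for the interim.
- **Section 8.1, multiplicity:** a one-sided 2.5% is split, "with 0.5%, 1.5% and 0.5% alpha allocated to the ORR, PFS and OS hypothesis, respectively".

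**The concern.** The first 210 subjects are, in the plan's own words, about 70% of ITT, so the two descriptions name different sets. Table 15 cannot be describing a second, later ORR analysis: 2.1 allows one, and 8.7.1 calls IA1 the final one. Section 8.1 describes itself as a summary and refers to 8.2 to 8.12 for the comprehensive plan. Within 8.2 to 8.12, the only place that assigns ORR a population is Table 15, and it says ITT. A programmer working from 8.6.1 would therefore use everyone randomized at the data cut.

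The choice matters because this test carries 0.5% alpha. If ORR is rejected, 8.8 passes its alpha on, and the footnote to Table 17 says the PFS and OS bounds depend on the ORR result. A subject randomized shortly before the cut adds to the denominator and almost certainly not to the numerator, so both response rates and their difference shrink for a reason unrelated to treatment.

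**Working it through.** **Inputs.** From 8.9: 55% v 30%, one-sided alpha 0.005, 210 subjects (105 per arm), 300 subjects in total, 14 months of enrollment. From Table 17: IA1 at about month 12, or 210 randomized plus 2 months. From Table 9: assessment every 28 days. From Appendix 12.7: response categories need two consecutive assessments. *Assumption:* accrual is uniform; the documents give no accrual pattern.

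**1. Reproduce the plan's figures on 210.** Power = Φ(Δ/SE − 2.576), with SE = √[(p₁q₁ + p₂q₂)/n].
SE = √[(0.2475 + 0.2100)/105] = 0.0660; 0.25/0.0660 = 3.787; Φ(3.787 − 2.576) = **88.7%**, as stated.
Pooled variance gives 87.0%, and exact enumeration of the unstratified Miettinen-Nurminen test gives 86.9%. With 30% in the control group, the smallest significant difference is 17.3 points, against the stated ~17. The stated power and bound therefore belong to a 210-subject analysis.

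**2. Subjects randomized by IA1.** Rate = 300/14 = 21.43 per month; the 210th is randomized at 210/21.43 = 9.8 months.

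| Cut-off | Further subjects | N randomized |
|---|---|---|
| 56 days after the 210th | 21.43 × 1.84 = 39 | 249 |
| 2 months after the 210th | 21.43 × 2 = 43 | 253 |
| Month 12 | 257 − 210 = 47 | 257 |

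If accrual is back-loaded (cumulative enrollment proportional to t^1.5 or t²; 2-month lag), the further subjects number about 60 or 78.

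**3. Can they count as responders?** The first two post-baseline assessments fall near days 29 and 57. With a 56-day lag and uniform accrual, about half of the further subjects would have one assessment and almost none would have the second. Section 8.4.1 defines ORR as a proportion of the analysis population, so these subjects are in the denominator and not the numerator, whether or not they are labelled missing.

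**4. Dilute and recompute.** Multiply both rates by 210/N, set n = N/2, and use the formula of step 1.

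| N | Rates | Difference (points) | Power, unpooled | Power, pooled |
|---|---|---|---|---|
| 210 | 55.0% v 30.0% | 25.0 | 88.7% | 87.0% |
| 249 | 46.4% v 25.3% | 21.1 | 83.6% | 82.0% |
| 253 | 45.7% v 24.9% | 20.8 | 83.2% | 81.6% |
| 257 | 44.9% v 24.5% | 20.4 | 82.8% | 81.2% |

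The N = 249 row in numbers: SE = √[(0.2487 + 0.1890)/124.5] = 0.0593; 0.2108/0.0593 = 3.556; Φ(0.980) = 83.6%. In the extreme case where all 300 were already randomized, unpooled power would be 78.9%.

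**5. Effect on the decision.** At N = 250 the bound is 15.3 points on the diluted scale, which is 15.3 × 250/210 = 18.2 points among the 210 assessable subjects, against 17.3 when only those 210 are analysed. A difference between 17.3 and 18.2 points would succeed under 8.1 and fail under Table 15.

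**6. Type I error.** Exact one-sided error with both arms at 30% diluted by 210/N: 0.0050 at N = 210, 0.0050 at N = 250, 0.0049 at N = 300.

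**The case against.** The best reply is that the plan identifies the analysis set several times and one table cell merely fails to repeat it. Section 8.1 says 210 twice, 8.9 powers on 210, and 8.7.1 and Table 17 time IA1 by the 210th subject. Table 15 has no column for the data cut, and ITT there may only mean analysed as randomized. On that reading, the first 210 of ITT, with missing counted as failure, fits every section. This stands as evidence of intent. It does not remove the conflict, because 8.5.1 gives ITT an explicit all-randomized meaning and nothing limits the ORR row to a subset.

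Four stronger readings are tempting and are not supported:

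- *That 8.5.1 itself places the ORR test on all randomized subjects.* It does not mention ORR. It names ITT for the primary efficacy analysis and supplies the definition; the assignment to ORR is made in Table 15.
- *That some 40 subjects are bound to be counted as failures.* The count rests on assumed accrual. The plan does not say whether an assessment not yet due is missing, and Appendix 12.7 lets the two consecutive assessments be made at any time, so an early unscheduled repeat could confirm a response. Almost none on schedule is as far as the documents go.
- *That the false-positive risk rises.* It does not under either set applied alone; the dilution is conservative.
- *That an all-randomized ORR analysis at IA2 needs relabelling.* None is planned: 8.7.1 limits IA2 to final PFS and interim OS.

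It is also fair to say that the practical effect is now small. Treatment closed after the 2017 clinical hold, and Section 8.0 allows the analysis to be modified and reported in the CSR. The report must still state one denominator.

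**Conclusion.** The conflict holds. Table 15 assigns the single confirmatory ORR analysis a population that differs from the one in 8.1 and from the 210-subject basis of the timing and power in 8.7.1 and 8.9. The 210-subject set is very probably the intended one, so Table 15 is the entry to correct.

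Applied literally, Table 15 would give expected rates of about 46% v 25% instead of 55% v 30% and power of about 83-84% instead of 88.7%, a loss of roughly 5 to 6 points. These figures assume uniform accrual, on-schedule assessments, and the plan's 55% and 30% holding in the first 210 at IA1. Back-loaded accrual would make the loss larger. The harm is an unfixed denominator, attenuated estimates and some lost power on a key secondary endpoint; type I error is unaffected.

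**What to change.** - In the ORR row of Table 15, replace ITT by: first ~210 randomized subjects, analysed as randomized (confirmatory test at IA1). Keep missing = non-responder within that set.
- State the same set in 8.7.1, so that the section fixes who is analysed as well as when.
- If ORR in all randomized subjects is reported later, call it descriptive. No additional analysis is required.

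The cost is wording only. Sample size, alpha split, bound and stated power are unchanged, because they were already computed on 210. Given the closed status of the trial, the CSR should name the same denominator.

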8.6.2 Statistical Methods for Safety Analyses

Safety and tolerability will be assessed by clinical review of all relevant parameters including adverse experiences (AEs), laboratory tests, vital signs, etc.

The analysis of safety results will follow a tiered approach ([Table 16](#)). The tiers differ with respect to the analyses that will be performed. “Tier 1” safety endpoints are those that will be subject to inferential testing for statistical significance with p-values and 95% confidence intervals provided for between-group comparisons. For this protocol, there are no Tier 1 events. Tier 2 parameters will be assessed via point estimates with 95%

confidence intervals provided for between-group comparisons; only point estimates by treatment group are provided for Tier 3 safety parameters.

Adverse experiences (specific terms as well as system organ class terms) that are not pre-specified as Tier-1 endpoints will be classified as belonging to "Tier 2" or "Tier 3", based on the number of events observed. Membership in Tier 2 requires that at least 4 subjects in any treatment group exhibit the event; all other adverse experiences and predefined limits of change will belong to Tier 3.

The threshold of at least 4 events was chosen because the 95% confidence interval for the between-group difference in percent incidence will always include zero when treatment groups of equal size each have less than 4 events and thus would add little to the interpretation of potentially meaningful differences. Because many 95% confidence intervals may be provided without adjustment for multiplicity, the confidence intervals should be regarded as a helpful descriptive measure to be used in review, not a formal method for assessing the statistical significance of the between-group differences in adverse experiences and predefined limits of change.

Continuous measures such as changes from baseline in laboratory, vital signs, that are not pre-specified as Tier-1 endpoints will be considered Tier 3 safety parameters. Summary statistics for baseline, on-treatment, and change from baseline values will be provided by treatment group in table format.

In addition, the broad clinical and laboratory AE categories consisting of the percentage of subjects with any AE, any drug related AE, any Grade 3-5 AE, any serious AE, any AE which is both drug-related and Grade 3-5, any AE which is both serious and drug-related, dose modification due to AE, and who discontinued due to an AE, and death will be considered Tier 2 endpoints. 95% confidence intervals (Tier 2) will be provided for between- treatment differences in the percentage of subjects with events; these analyses will be performed using the Miettinen and Nurminen method (1985), an unconditional, asymptotic method.

To properly account for the potential difference in follow-up time between the study arms, which is expected to be longer in the pembrolizumab containing arms, AE incidence density adjusted for treatment exposure analyses may be performed as appropriate. Based on emerging external data, the supportive analysis strategy for safety parameters may be modified to improve the integrity and efficiency of the design. Should this happen, the change will be documented in supplemental SAP, if not in a protocol amendment, at the earliest time before any unblinding of the data.

Table 16 Analysis Strategy for Safety Parameters

Safety Tier	Safety Endpoint	95% CI for Treatment Comparison	Descriptive Statistics
Tier 2	Any AE	X	X
	Any Grade 3-5 AE	X	X
	Any Serious AE	X	X
	Any Drug-Related AE	X	X
	Any Serious and Drug-Related AE	X	X
	Any Grade3-5 and Drug-Related AE	X	X
	Dose Modification due to AE	X	X
	Discontinuation due to AE	X	X
	Death	X	X
		Specific AEs, SOCs (including ≥ 4 of subjects in one of the treatment groups)	X
Tier 3	Specific AEs, SOCs (incidence < 4 of subjects in all of the treatment groups)		X
	Change from Baseline Results (Labs, ECGs, Vital Signs)		X

Time to Grade 3-5 AE

In addition to tiered approach, exploratory analysis will be performed on time to first Grade 3-5 AE. Time to first Grade 3-5 AE is defined as the time from the first day of study drug to the first event of Grade 3-5 AE. The Kaplan-Meier method will be used to estimate the curve of time to first Grade 3-5 AE. The treatment difference in time to first Grade 3-5 AE will be assessed by the unstratified log-rank test. An unstratified Cox proportional hazards model with Efron's method of tie handling will be used to assess the magnitude of the treatment difference (ie, the hazard ratio). The hazard ratio and its 95% confidence interval from the unstratified Cox model with a single treatment covariate will be reported. More details will be described in supplemental SAP.

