2.0 TRIAL DESIGN

2.1 Trial Design

This is a randomized, active-controlled, multicenter, open label trial of pomalidomide (Pom) and low dose dexamethasone (Dex) with or without pembrolizumab (MK-3475) in subjects with refractory or relapsed and refractory multiple myeloma (rrMM) who have undergone at least 2 lines of prior treatment, are refractory to their last line of treatment and have been previously exposed to an immunomodulatory drug (IMiDs) such as lenalidomide or thalidomide and a proteasome inhibitor such as bortezomib, ixazomib, or carfilzomib. Subjects should be considered to be refractory or relapsed and refractory to an IMiD or a proteasome inhibitor or both. Subjects will be stratified based on the number of prior lines of treatment (2 vs. ≥ 3) and disease status (refractory vs. sensitive to lenalidomide).

Approximately 300 subjects will be enrolled in this trial to examine the safety and efficacy of pembrolizumab 200 mg fixed dose administered every 3 weeks (Q3W) in combination with pomalidomide 4 mg daily on days 1 to 21 and low dose dexamethasone 40 mg on days 1, 8, 15 and 22 of repeated 28-day cycles compared to pomalidomide 4 mg daily on days 1 to 21 and low dose dexamethasone 40 mg on days 1, 8, 15 and 22 of repeated 28-day cycles. Cross-over between the arms is not permitted. Adverse events will be monitored throughout the trial and graded in severity according to the guidelines outlined in the National Cancer Institute (NCI) Common Terminology Criteria for Adverse Events (CTCAE) version 4.0. In both arms, treatment on trial will continue until documented confirmed disease progression, unacceptable adverse event(s) (AEs), intercurrent illness that prevents further administration of treatment, subject withdraws consent, pregnancy of the subject, noncompliance with trial treatment or procedure requirements or administrative reasons.

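### Tier 2 adverse-event contrasts are committed only as crude percentages, although the plan expects longer follow-up on pembrolizumab and leaves exposure adjustment optional

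*Combined protocol and SAP*

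**What the plan says.** Section 8.6.2 sorts safety parameters into tiers and names no Tier 1 events. Tier 2 holds the broad AE categories (any, drug-related, Grade 3-5, serious, their combinations, dose modification, discontinuation, death) and any specific term reported in at least 4 subjects in an arm. Its 95% confidence intervals are for between-treatment "differences in the percentage of subjects with events; these analyses will be performed using the Miettinen and Nurminen method (1985").

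The next paragraph raises "the potential difference in follow-up time between the study arms, which is expected to be longer in the pembrolizumab containing arms", and answers it with a permission: "AE incidence density adjusted for treatment exposure analyses may be performed as appropriate". It gives no trigger, event list, denominator or estimator.

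Three other statements bear on the point:

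- Section 8.6.2 says of the many unadjusted intervals that "the confidence intervals should be regarded as a helpful descriptive measure to be used in review", and that they are not a formal test.
- The same section commits to one time-to-event safety analysis: "exploratory analysis will be performed on time to first Grade 3-5 AE", by Kaplan-Meier, log-rank and Cox.
- Death, also a Tier 2 item, is analysed as OS by stratified log-rank and Cox (Section 8.6.1).

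Section 8.12 summarises exposure in cycles but does not link it to AE incidence.

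**The concern.** Observation time for adverse events depends on how long treatment lasts. Section 2.1 states: "In both arms, treatment on trial will continue until documented confirmed disease progression". Section 7.2 collects AEs until 30 days after treatment stops, and Section 7.2.3.1 collects serious AEs until 90 days after, or 30 days if new anticancer therapy starts. An arm with longer PFS is therefore watched for longer. Only Arm A may be treated beyond certain progressions (Section 7.1.2.8.6), which can lengthen its exposure further.

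A crude percentage of subjects ever affected mixes how often the event occurs with how long subjects were watched. If the combination delays progression, equal toxicity looks like excess toxicity. If Arm A stops sooner, real excess toxicity is understated. The plan foresees the imbalance but fixes no response to it, so the adjustment could be run or left out after the results are known. The treatment phase was closed on safety grounds, so the choice matters in either direction.

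**Working it through.** **Inputs.** All from Section 8.9 unless noted: exponential PFS with control median 4 months; PFS hazard ratio 0.635; 236 PFS events at about month 20; accrual over 14 months; 300 subjects, 1:1. The 30- and 90-day windows come from Sections 7.2 and 7.2.3.1. The documents give no AE rate, so control incidence is varied.

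**Reproducing the plan's figures.** PFS power = Φ(√236/2 × |ln 0.635| − z(0.985)) = Φ(7.681 × 0.4541 − 2.170) = Φ(1.318) = 90.6%, as stated. With 5% yearly dropout, 235.9 PFS events are expected at month 20 (stated: about 236).

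**Model.** Time on treatment follows PFS, with stopping rate m = ln 2/4 = 0.1733 per month in control and 0.635 × 0.1733 = 0.1100 in Arm A (median 4/0.635 = 6.3 months). The same constant AE hazard L applies in both arms.

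**Simplest case** (complete follow-up, no window): P(at least one AE) = L/(L + m). For 30% in control, L = 0.1733 × 0.3/0.7 = 0.0743, and Arm A shows 0.0743/(0.0743 + 0.1100) = 40.3%. The largest possible excess is (1 − √0.635)/(1 + √0.635) = 11.3 points.

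**With the collection window w and a data cut at month T:** P = ∫ L·exp(−Lt)·S(t) dt from 0 to T, where S(t) = exp(−m·max(0, t − w)) × min(14, T − t)/14 is the chance of still being under AE collection at t. L is set to give the stated control incidence and then applied to Arm A. PFS dropout is ignored.

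Crude excess in Arm A, in percentage points, with identical hazards:

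| Control incidence | 10% | 20% | 30% | 50% | 70% | 90% | Maximum |
|---|---|---|---|---|---|---|---|
| Complete follow-up, no window | 4.9 | 8.2 | 10.3 | 11.2 | 8.6 | 3.4 | 11.3 |
| Complete follow-up, 30 days | 4.2 | 7.2 | 9.0 | 9.9 | 7.8 | 3.2 | 10.0 |
| Month 30, 30 days | 3.6 | 6.3 | 8.3 | 9.7 | 7.7 | 3.2 | 9.7 |
| Month 20, 30 days | 2.5 | 4.5 | 6.1 | 7.8 | 7.0 | 3.1 | 7.9 |
| Month 20, 90 days (serious AEs) | 1.6 | 2.9 | 4.0 | 5.2 | 4.9 | 2.5 | 5.3 |

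The last row gives every subject the full 90 days. Where new therapy shortens the window, the figure moves towards the row above.

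**Sensitivity at month 20, 30-day window.**

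- PFS hazard ratio 0.8: at most about 4 points. Ratio 1.0: zero. Ratio 1.25 (Arm A stops sooner): about −4 points at 50% control incidence.
- Extra stopping of 0.05 per month in both arms: maximum 6.1 points.
- Hazard confined to the first 1 to 3 months: at most about 1.5 points for control incidences up to 50%. With complete follow-up and no window it is 0.2 to 4.3 points for incidences of 5 to 60%.

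**Scale.** The 95% half-width at 50% incidence with 150 per arm is 1.96 × √(2 × 0.5 × 0.5/150) = 11.3 points, so the bias can approach the size of the interval's half-width.

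**Person-time rates as the alternative.** With a constant hazard the rate ratio is 1 in every row. With identical hazards confined to the first 1 to 3 months it is about 0.79 to 0.85 for control incidences up to 50%: later event-free time in Arm A dilutes the rate, and equal toxicity looks 15 to 21% lower on pembrolizumab.

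**The case against.** The strongest reply is that the plan never lets these intervals decide anything. Safety is assessed by clinical review, there are no Tier 1 events, and the Tier 2 intervals are declared descriptive. Crude incidence also answers a legitimate question: what proportion of subjects had this event on the assigned regimen. This stands. A reader might convert the excess into a frequency of intervals excluding zero (47% of trials at 30% v 40.3%) and set it against a nominal 5%. The documents do not support that reading, because no test is planned.

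The reply continues that the imbalance is only an expectation. It needs a PFS benefit, stopping mainly at progression, and a roughly constant hazard. The treatment phase was closed early, which truncates exposure in both arms, and Section 8.0 allows the analyses to be modified. This also stands, and it limits the size. It does not remove the gap, because early closure could shrink or reverse the imbalance and a fixed rule protects in both directions.

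Third, time-aware analyses already exist for Grade 3-5 AEs and death. That is correct, but serious AEs, drug-related AEs of any grade, dose modification, discontinuation due to AE and specific terms have no committed equivalent.

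Last, making person-time rates the main comparison would bring in the opposite bias for early-onset events. This is right and shapes the fix.

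**Conclusion.** The point holds as a cheap improvement. For most Tier 2 items the plan commits only to a between-arm contrast that its own expectation of unequal follow-up would bias. Under the design PFS assumptions, a constant equal hazard and the 30-day window, the spurious excess is about 2.5 to 8 points at month 20 for control incidences of 10 to 70%, and up to about 10 points with longer follow-up. It peaks for events of mid-range frequency. For serious AEs with the 90-day window it is at most about 5 points at month 20. It is near zero for early-onset events, zero with equal exposure, and negative if Arm A stops sooner.

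Two stronger readings are not supported. One is that every category would be inflated by about 10 points: that is close to the ceiling for mid-frequency events with long follow-up. The other is that unequal exposure explains the safety findings behind the clinical hold: the documents contain no AE or exposure results from this trial.

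**What to change.** In Section 8.6.2, replace the permission with a commitment:

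- **Main time-aware contrast.** For each broad Tier 2 AE category, and for specific Tier 2 terms where numbers allow, report Aalen-Johansen cumulative incidence at a fixed time, with the between-arm difference and 95% CI. Six months is a workable example, since it equals the planned minimum follow-up. Under the design assumptions exp(−0.1733 × 5.01) = 42% of control and exp(−0.1100 × 5.01) = 58% of Arm A subjects would still be under AE collection then.
- **Competing event and censoring.** Treat death as the competing event. Censor at the end of the collection window: 30 days for AEs, 90 days for serious AEs, or earlier if new therapy starts. Section 7.2.3.1 words the new-therapy rule in two ways, so name the one used. Do not treat stopping treatment as a competing event, because that would keep part of the exposure effect. State that the method assumes collection ends independently of AE risk.
- **Supportive.** Report exposure-adjusted first-event rates, with a note that they dilute early-onset events.
- **Retain** the crude percentages and their Miettinen-Nurminen intervals alongside.

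The cost is SAP wording and extra tables from AE onset and dosing dates. Any such analysis specified after treatment-level safety results were known should be labelled as such in the CSR.
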